12.4. VITAL SIGNS

Observed and change from baseline values will be summarized by visit using descriptive statistics.

Box plots of change from baseline by visit and group will be presented for measurements. The whiskers will display the 5th and 95th percentiles and outliers will be identified on the plot with subject ID. The number of observations contributing to each visit box plot will be included.

The number and percentage of subjects with an increase or decrease from baseline in systolic blood pressure of <10 mmHg, ≥ 10 to <20mmHg, ≥ 20 to <30 mmHg or ≥ 30 mmHg will be summarized by visit. The denominator for percentages will be the number of subjects still on-treatment. This summary will be repeated for diastolic blood pressure using the following categories <5 mmHg, ≥ 5 to <10 mmHg, ≥ 10 to <15 mmHg, ≥ 15 to <20 mmHg, ≥ 20 to <25 mmHg or ≥ 25 mmHg.

Observed and change from baseline values will be listed. The listing will identify the increase or decrease from baseline categories detailed above for systolic and diastolic blood pressure.

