8.2. GENERAL METHODS

Continuous variables will be summarized using the number of non-missing observations (n), mean, SD, median, minimum, and maximum. Categorical variables will be summarized using counts and percentages.

Unless otherwise specified, the estimated mean and median for a set of values should be displayed to 1 more decimal place than the original values, and SD should be displayed to 2 more decimal places than the original values. The minimum and maximum should be displayed to the same number of decimal places as the original values. Deviations from this convention may arise to take account of the relevance of the precision (e.g., the distance walked in the 12MWT is reported to the nearest cm, but there is no relevance in presenting the mean to the nearest mm). These deviations from convention will be documented in the relevant analysis sections below.

Percentages will be displayed with 1 decimal place; except percentages will not be presented when the count is zero and 100% will be presented as an integer. Unless stated otherwise, percentages of subjects will be based on the number of subjects with non-missing data in the analysis set used for the presentation.

Unless stated otherwise, an on-treatment measurement will be any measurement collected (including scheduled and unscheduled visits) up to the date of last dose plus one day. Drug interruptions will not be considered, i.e., data will not be excluded during a drug interruption if the subject resumes study treatment; this includes the follow-up period for subjects who enrol in REN001-202 at the REN001-201 FU.

In by-visit summary tables, the baseline will be summarized using all available data, but also for each visit using only the baseline data from subjects with available data at the visit; hence the mean change from baseline will equal the mean observed visit value – mean baseline value.

Throughout this document ‘change from baseline’ refers to the actual change from baseline (i.e., observed visit value – baseline value). The baseline definitions are detailed in [Section 8.6](#).

There will be 3 approaches to summarising the data and, unless stated otherwise, all presentations will be presented for each approach. [Figure 1](#) in [Section 2](#) shows the different pathway options a subject can enter REN001-202 and the 5 distinct reporting groups these

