8.4. VISIT WINDOWS

Data will be assigned to ‘analysis’ visits using windowing (see table below). If more than one assessment (including the early termination or unscheduled assessments) falls within the same defined window, the on-treatment assessment closest to the target day with non-missing data will be used for analysis. If the scheduled visit assessment is on-treatment and within the analysis window, then this will be used irrespective of other unscheduled assessments within the analysis window. If two assessment dates are at the same distance from the target day, the latest on-treatment assessment with non-missing data will be used for analysis. Off-treatment assessments will only be assigned to a visit window in the absence of an on-treatment assessment within the analysis window.

This is the same approach as used in the REN001-201 SAP and therefore the REN001-201 data will have the same analysis visit windowing assigned as per the REN001-201 CSR.

To assess whether a REN001-202 visit is within the analysis window the day relative to the start of REN001-202 will be used. This will mean that for subjects who enrol at REN001-201 FU the interruption in study drug during the REN001-201 FU period will be ignored.

Study	Original Visit	Visit Name for Combined Study Summaries	Target Day ¹	Protocol Visit Window	Analysis Window ¹	Analysis Interval
REN001-201	Baseline	Baseline	1	NA	≤1*	NA
	Week 2	Month 0.5	14	±3	8 – 20	13 (±6)
	Week 4	Month 1	28	±3	21 – 35	15 (±7)
	Week 12	Month 3	84	±7	63 – 105	43 (±21)
	Week 18	Month 4.5	126	±7	106 – 146	41 (±20)
	Week 24	Month 6	168	±7	147 – 189	43 (±21)
REN001-202	Baseline	Month 6	1	NA	≤1*	NA
	Month 1	Month 7	28	±3	21 – 35	15 (±7)
	Month 3	Month 9	84	±7	63 – 105	43 (±21)
	Month 6	Month 12	168	±7	147 – 189	43 (±21)
	Month 9 [^]	Month 15 [^]	252	±21	211 – 293	83 (±41)
	Month 12	Month 18	336	±21	294 – 378	85 (±42)
	Month 15 [^]	Month 21 [^]	420	±21	379 – 461	83 (±41)
	Month 18	Month 24	504	±21	462 – 546	85 (±42)
	Month 24	Month 30	672	±21	630 – 714	85 (±42)
	Month 30	Month 36	840	±21	798 – 882	85 (±42)
	Month 36	Month 42	1008	±21	966 – 1050	85 (±42)
	Month 42	Month 48	1176	±21	1134 – 1218	85 (±42)
	Month 48	Month 54	1344	±21	1302 – 1386	85 (±42)

NA=not applicable.

¹ Target day and analysis windows are relative to start of each study.

* Baseline values must be prior to dosing if time of assessment is recorded.

[^] Month 9 and Month 15 (original) visits are only applicable for German sites.

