Subjects can have more than one baseline defined depending on which reporting group is used. [Section 8.6](#) provides more details on the baseline definitions.

REN001-202 follow-up visit, by design, is after the last dose of study drug and should not be allocated to on-treatment visits. Similarly, REN001-201 follow-up visit should not be assigned to an on-treatment visit in REN001-202.

Windowing will not be used for the DXA scan data. Subjects can have a maximum of 4 DXA scans across the studies and these will be assigned to the nominal scheduled visits.

If an unscheduled or early termination visit is mapped to a scheduled visit, then the type of visit will be identified in the appropriate listing together with the visit that it has been mapped to. In addition, data collected outside these windows will not be attributed to an analysis window and will only be listed, unless specified otherwise in [Section 10](#) and [Section 10](#). Any scheduled visit outside the window will be identified on the appropriate listing.

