10.3. PATIENT GLOBAL IMPRESSION OF CHANGE (PGIC) – MUSCLE SYMPTOMS AND FATIGUE SYMPTOMS

PGIC muscle symptoms and fatigue symptoms scores will be summarized by visit as a categorical variable. The table will include categories for withdrawn and missing. Percentages will not be presented for the withdrawn and missing rows, and the percentages presented will use the number of non-missing values as the denominator.

Stacked bar charts will be presented for the proportion of subjects at each of the PGIC scores by visit for each of the groups. The categories will include each of the PGIC levels and missing and withdrawn.

10.4. PATIENT GLOBAL IMPRESSION OF SEVERITY (PGIS) SCORE - MUSCLE SYMPTOMS AND FATIGUE SYMPTOMS

Categorical shift tables from baseline at each visit will be summarized including marginal totals. The table will include categories for withdrawn and missing. Percentages will not be presented for the withdrawn and missing rows, and the percentages presented will use the number of non-missing values as the denominator. In addition, to account for subjects at the extreme ends of the scale, the shift table will be repeated for improvement or worsening from baseline at each visit, based on those subjects who have the potential to improve or worsen, respectively.

Stacked bar charts will be presented for the proportion of subjects at each of the PGIS scores by visit for each of the groups. The categories will include each of the PGIS levels and missing and withdrawn.

10.5. PATIENT-REPORTED OUTCOMES MEASUREMENT INFORMATION SYSTEM (PROMIS) SHORT FORM – FUNCTIONAL ASSESSMENT OF CHRONIC ILLNESS THERAPY (FACIT) FATIGUE 13A

Observed and change from baseline values will be summarized by visit using descriptive statistics for the T-score. The associated 95% confidence intervals for the observed and change from baseline means will also be presented. The number of subjects withdrawn prior to the visit or with missing data will also be presented.

Mean plots of observed and change from baseline values for the T-score, with 95% confidence intervals will be presented by group with visit on the x-axis. A reference line for no change (i.e., $y=0$) will be included in the change from baseline plot.

Spaghetti plots for the changes from baseline will be plotted over time. The plots will be split by group. The y-axis will be uniform across the plots to allow comparisons. A reference line for no change (i.e., $y=0$) will be included.

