13. INTERIM ANALYSES

An interim synoptic CSR will be prepared for this study to be included in the regulatory submission package. The data cut will be the date of the last subject last visit in REN001-201 and the data will be extracted from the database after REN001-201 database has been locked. This CSR will include all REN001-202 data up to the data cut date and best efforts will be made to clean data up to this data cut date.

There will be a reduced set of safety outputs generated after submission for the 120-day safety update which is required as part of the submission package. The final CSR will occur after all subjects have had the ability to complete REN001-202, the data has been cleaned and the database locked.

An independently chaired Safety Review Committee (SRC) will review safety data at specified intervals for the duration of the study. The structure, function and operation of the SRC is detailed in the REN001-202 SRC charter. The SRC review of safety data will be limited to data from REN001-202 and will not be combined with REN001-201 data.

**14. CHANGES FROM PLANNED ANALYSES SPECIFIED
IN THE PROTOCOL**

None.

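### The by-visit blood-pressure change categories are divided by subjects still on treatment, not by the subjects measured at the visit, so numerator and denominator come from different records

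*SAP*

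**What the plan says.** SAP section 12.4 plans a by-visit table of "The number and percentage of subjects with an increase or decrease from baseline in systolic blood pressure", in bands from below 10 mmHg to 30 mmHg or more, and repeats it for diastolic pressure with its own bands. The denominator is given in one sentence: "The denominator for percentages will be the number of subjects still on-treatment". No missing row is specified.

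Other parts of the SAP bear on that sentence:

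- **Default denominator (section 8.2).** Unless stated otherwise, "percentages of subjects will be based on the number of subjects with non-missing data in the analysis set". Section 12.4 is therefore a stated exception.
- **Comparable tables.** The PGIC table (section 10.3) has withdrawn and missing rows, and "the percentages presented will use the number of non-missing values as the denominator". The PGIS, PROMIS, SF-36, BPI and phenotype tables follow the same rule. The laboratory and ECG shift tables (sections 12.2 and 12.5) carry a missing category.
- **Meaning of on-treatment (section 8.2).** It is defined for a measurement: "an on-treatment measurement will be any measurement collected (including scheduled and unscheduled visits) up to the date of last dose plus one day". It is not defined for a subject at a visit.
- **Visit windows (section 8.4).** "Off-treatment assessments will only be assigned to a visit window in the absence of an on-treatment assessment within the analysis window". Also, "data collected outside these windows will not be attributed to an analysis window and will only be listed".
- **Interim report (section 13).** "This CSR will include all REN001-202 data up to the data cut date".

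**The concern.** A percentage is readable when the people who could be counted are the people in the denominator. Here they are not. On-treatment subjects who missed the visit, or attended outside the window, are in the denominator but cannot appear in any category. Conversely, a subject who has stopped treatment may have a value that fills the window and is counted, although that subject is no longer in the denominator. The second case is realistic: Protocol sections 6.9 and 6.13 place the early-withdrawal visit as soon as possible after the last dose, and any value more than one day after that dose is off-treatment.

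The incidence of potentially clinically significant vital-sign changes is a secondary endpoint (SAP section 3.2.2). The SAP sets criteria of potential clinical importance for certain laboratory tests (section 12.2) and QTcF (section 12.5), but none for vital signs. This table is thus the only categorical output for that endpoint, in a study whose primary objective is safety.

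**Working it through.** The documents give no blood-pressure percentage, missing-data rate or count at the data cut, so there is no planned figure to reproduce. The rates below are assumptions chosen to show size and direction. I also assume that each measured subject falls in exactly one category.

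**1. Missing or out-of-window values in on-treatment subjects.**

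Printed % = (% among measured) × (measured ÷ on-treatment).

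Take 150 subjects on treatment (the planned mtDNA number, SAP section 3.5) and 10% of measured subjects in a given category.

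| Without a usable value | Measured | In category | Printed % | Categories sum to |
|---|---|---|---|---|
| 0% | 150 | 15 | 15/150 = 10.0% | 100% |
| 5% | 142.5 | 14.25 | 14.25/150 = 9.5% | 95% |
| 10% | 135 | 13.5 | 13.5/150 = 9.0% | 90% |
| 20% | 120 | 12 | 12/150 = 8.0% | 80% |

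The relative loss equals the missing fraction, whatever the group size or category rate. At 20% missing, 5% becomes 4.0% and 20% becomes 16.0%. With 50 subjects (the planned nDNA maximum) the percentages are the same.

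**2. Off-treatment values in the window.**

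Take 100 subjects on treatment, all measured, plus k off-treatment values assigned to the window, with 10% of all values in the category.

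- k = 5: 0.10 × 105 ÷ 100 = 10.5%; categories sum to 105%.
- k = 10: 0.10 × 110 ÷ 100 = 11.0%; categories sum to 110%.
- 5 on-treatment values missing and 5 off-treatment values added: 0.10 × (95 + 5) ÷ 100 = 10.0%. The two errors cancel and neither shows.

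**3. Two readings of the denominator at an interim cut.**

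Take 10% among measured and 5% missing among those who have reached the visit.

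- If it means on treatment at that visit: 10% × 0.95 = 9.5%, however many subjects have yet to reach it.
- If every ongoing subject counts: 10% × 0.95 × (share who have reached the visit). With 25%, 50% or 75% not yet there, this gives 7.1%, 4.75% or 2.4%.

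The SAP does not choose between the two readings.

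**4. With the section 8.2 default.** The denominator is the number measured, so 10% among measured prints as 10.0% at any level of missingness and the categories sum to 100%.

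**The case against.** The strongest reply has four parts.

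**The choice is explicit and permitted.** Section 8.2 allows exceptions, so section 12.4 does not contradict it. That stands. But no reason is given, and the exception yields percentages that need not sum to 100%.

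**The effect can be undone by a reader.** Counts are printed beside percentages, by-visit summaries give n, the box plots in section 12.4 show the number of observations, the listings flag each subject's category, and section 9.1 tabulates attended and missed visits. No test or decision rule depends on this table. All of this stands, and it limits the importance of the point.

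**Interim dilution is not established.** A reader might infer that the interim report will heavily understate these changes because every ongoing subject is in the denominator. The documents do not support that as fact. In a by-visit table, the natural meaning may be on treatment at that visit. Section 9.5 sets an ongoing subject's last dose at the last contact up to the cut; applied here, that would exclude subjects not yet at the visit. Section 9.1 restricts the interim attendance table to subjects who could have reached the visit. Neither rule is extended to section 12.4, so the term is open. The size would also depend on accrual, which no document gives, and the SAP does not say that this table will be in the synoptic interim report.

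**The direction is not only downward.** A reader might infer that all missing data dilute the percentage, that only large changes are understated, or that the problem grows at later visits. None of these follows. Subjects who stop treatment leave the denominator, so their missing values do not dilute. Every category shrinks, including the smallest changes. Off-treatment values act upwards. Growth over time would need rising missingness among subjects still on treatment, and nothing in the documents shows that. If the programmer also restricted the numerator to on-treatment values, the upward effect would vanish, but section 12.4 does not say so.

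**Conclusion.** The point holds as a mismatch between numerator and denominator in one descriptive safety table. The downward effect equals the fraction of on-treatment subjects without a usable value: at an assumed 10%, a printed 9.0% in place of 10.0%. Off-treatment values can offset or reverse it. At an interim cut the denominator is undefined rather than shown to be wrong. Counting everyone ongoing would dilute more, but that is one reading and its size rests on assumed accrual. No other analysis is affected. The point is still worth acting on before database lock, because the table alone serves the vital-sign incidence endpoint and the SAP already has a default that works.

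**What to change.** Replace the denominator sentence in SAP section 12.4, for both systolic and diastolic pressure, with:

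> The denominator is the number of subjects with a non-missing baseline and an on-treatment value in that visit window; numerator and denominator use the same records.

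Print n for each visit and add a missing row. At interim cuts, also show the number of subjects with the potential to reach the visit, using the rule already in section 9.1.

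The cost is one SAP sentence and a small change to the table shell; section 2 allows SAP amendments until database lock. There are two consequences. Percentages may become slightly less favourable where missing values had diluted them. Off-treatment blood-pressure changes would no longer be counted in this table, so their categories would appear only in the listing.

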12.5. ECG

Observed and change from baseline values will be summarized by visit using descriptive statistics.

A shift table from baseline to visit, for overall ECG interpretation (normal, abnormal not clinically significant, abnormal clinically significant and missing) will be summarised with marginal totals, using counts and percentages.

A shift table from baseline to the maximum post baseline QTcF value will be summarized according to the categories specified in the table below. The maximum will be taken from all scheduled and unscheduled on-treatment values.

Parameter	Criteria
QTcF	
< 450 msec
 
≥ 450 msec and < 480 msec*
 
≥ 480 msec and < 500 msec*
 
≥ 500 msec*

QTcF increase from baseline	
< 30 msec
 
≥ 30 msec and < 60 msec*
 
≥ 60 msec*

* Values of PCI.

Observed and change from baseline values will be listed. The listing will identify QTcF values of PCI (identified in the above table).

12.6. PHYSICAL EXAMINATION

Physical examination data will be listed.

12.7. EYE EXAMINATION

Observed and change from baseline values for the 4 cataract gradings in LOCS III (nuclear opalescence, nuclear colour, cortical and posterior subcapsular cataracts) will be summarized by visit using descriptive statistics. The summary will be across both eyes (i.e., each subject will contribute 2 values if they have a left and right eye reading at the visit) and repeated for the worst change at each visit.

Eye examination data will be listed. Eye examination data will be listed separately - refraction, BCVA, pinhole visual acuity, slit lamp examination, cataract grading, tonometry and irido-corneal drainage angle assessment.

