3.2.2 Secondary Endpoints

For mtDNA and nDNA subjects:

- Absolute values, changes from baseline, and incidence of potentially clinically significant changes in:
 - Laboratory safety tests
 - Electrocardiograms (ECG)
 - Supine vital signs
 - Eye assessments

For mtDNA subjects:

- Absolute values and changes from baseline in:

- Distance walked during the 12MWT*
- MFIS total scores and sub-scale scores*

Patient Global Impression of Severity (PGIS) scores for fatigue and muscle symptoms

- Brief pain inventory (BPI) pain severity and pain interference scores*
 - Patient Reported Outcomes Measurement Information System (PROMIS) Short Form- Functional Assessment of Chronic Illness Therapy (FACIT) Fatigue 13a scores*
 - 36-Item Short Form Health Survey (SF-36) domain scores (7-day recall)*
 - Work Productivity and Activity Impairment Questionnaire: Specific Health Problem (WPAI:SHP) scores*
 - First 6-minute walk distance and last 6-minute walk distance*
 - Phenotypic description questions*
- Patient Global Impression of Change (PGIC) scores for fatigue and muscle symptoms

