7.1.6 Eye Examination

All eye examinations should be carried out by an appropriately qualified professional. Best efforts should be made to ensure the same professional undertakes the slit lamp examinations for a particular subject in both the STRIDE study and in this long-term safety study. If the lens is clear, that should be recorded. If a cataract is identified, the cataract should be

classified and graded against the Lens Opacity Classification System III, ([Chylack et al, 1993](#)).

In addition, best corrected distance visual acuity (including refraction) should be assessed.

For scheduling reasons, the above assessments may be conducted \pm 14 days of the visit window given for the eye assessments.

In addition, any subject who experiences any visual symptoms during the study should have an additional eye examination as appropriate.

Eye examinations will not be repeated if within 6 months of a previous test within STRIDE.

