8.6 Safety Analyses

No imputation will be used for handling missing data, with the exception of conservative approaches taken for missing AE information (e.g., intensity). Details of such conventions will be documented in the SAP.

Treatment-emergent adverse events will be summarized by SOC and Preferred Term, in accordance with the MedDRA coding dictionary. The number of subjects reporting each AE preferred term will be tabulated for all TEAEs and separately for those considered as at least possibly related to study treatment by the Investigator. Number of subjects reporting SAEs and AESIs will also be tabulated.

Changes from baseline in laboratory parameters (including bone and calcium markers), vital signs, ECG and eye examinations data will be summarized by visit.

The incidence of potentially clinically significant laboratory and ECG values (e.g., increase in QTcF ≥ 30 msec from baseline or an absolute QTcF value of ≥ 500 msec).

Absolute values and changes from baseline for the DXA endpoints will be summarized. Summaries will be presented over all subjects and for the following demographic sub-groups:

- Men
- Pre-menopausal women
- Post-menopausal women

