3.2.2. Secondary Endpoints

- Absolute values, changes from Baseline and incidence of potentially clinically significant changes in:

- Laboratory safety tests
- Electrocardiograms (ECGs)
- Vital signs
- Eye assessments

For mtDNA-PMM subjects

- Absolute values and changes from Baseline in:
 - Distance walked during the 12-minute walk test (12MWT)*
 - Modified Fatigue Impact Scale (MFIS) Total scores and sub-scale scores*
 - Patient Global Impression of Severity (PGIS) score for fatigue and muscle symptoms
 - Brief Pain Inventory (BPI) pain severity and pain interference scores*
 - Patient-Reported Outcomes Measurement Information System (PROMIS) Short Form – Functional Assessment of Chronic Illness Therapy (FACIT) Fatigue 13a scores*
 - 36 Item Short Form Survey (SF-36) domain scores (7-day recall)*
 - Work Productivity and Activity Impairment questionnaire: Specific Health Problem (WPAI:SHP) scores*
 - First 6-minute walk distance and last 6-minute walk distance*
 - Phenotypic description questions
- Patient Global Impression of Change (PGIC) scores (muscle and fatigue symptoms)

**Collected up to Month 24 only.*

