6.7. EYE EXAMINATIONS

Eye examination data will be performed during the study by an appropriately qualified professional. Any abnormality considered clinically significant, will be reported as an AE.

To allow for scheduling of the eye examinations the REN001-201 Week 24 (Month 6) assessment can occur up to 14 days after the visit. Hence, this examination could occur after the start of administration of mavodelpar in REN001-202; this period is not considered sufficient time to have an impact on eye examination results. Therefore, for those mtDNA-PMM subjects who received placebo in REN001-201, enrolled in REN001-202 at REN001-201 Exit, enrol from study REN001-101 or for nDNA-PMM subjects this record will still be considered the baseline record relative to the start of mavodelpar provided it occurs within 14 days of the first dose of mavodelpar.

Baseline eye examinations will not be required for REN001-201 Exit subjects if the screening visit is within 6 months of the last REN001-201 examination.

Best corrected visual acuity (BCVA) can be assessed using the LogMAR scale, ETDRS letters or Snellen line. All results will be converted to the LogMAR scale before calculating changes from baseline at each visit for left and right eye BCVA (Roy 2003).

Where the Snellen scale has data recorded as x/y the MAR value is calculated by dividing y by x and then the LogMAR is the base 10 logarithm of the MAR value [i.e., $\text{LogMAR} = \log_{10}(\text{MAR})$]. Hence, higher scores indicate worse BCVA and increases from baseline indicate deterioration.

A change of 0.02 in LogMAR is equivalent to 1 letter. Hence, a Snellen scores with ‘-z’ or ‘+z’ indicating z letters fewer, or z letters more, respectively, will require an adjustment to the LogMAR score; 0.02 will be added or subtracted, respectively, for each letter (z).

e.g.,

$$20/15-1: \text{LogMAR} = \text{Log}_{10}(15 \text{ divided by } 20) + 0.02 = -0.105$$

$$20/15+1: \text{LogMAR} = \text{Log}_{10}(15 \text{ divided by } 20) - 0.02 = -0.145$$

If the Snellen scale is not reported in x/y format or x/y±z format, then the conversion to logMAR will not be done.

A change of 0.3 LogMAR (equivalent to 15 letters or 3-line change) is considered meaningful.

Refraction error based on spherical equivalent will be derived for each eye using the following formula:

$$\text{Spherical Equivalent (diopters)} = \text{cylinder (diopters)}/2 + \text{sphere (diopters)}$$

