Changes from baseline at each visit will be calculated.

Cataract are classified and graded against the Lens Opacity Classification System III (LOCS III) for nuclear opalescence, nuclear colour, cortical and posterior subcapsular cataracts. Changes from baseline will be calculated. Higher scores equate to a deterioration in cataracts. The largest increase from baseline (or smallest decrease if both eyes show a reduction from baseline) across the eyes will be identified at each visit.

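### SAP 12.7 gives no examination-based incidence count for eye changes, a stated secondary endpoint, and its LOCS III change summaries as written omit eyes that were clear at baseline

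*SAP*

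**What the plan says.** Protocol 3.2.2 defines a secondary endpoint for mtDNA and nDNA subjects as "Absolute values, changes from baseline, and incidence of potentially clinically significant changes in" four safety domains: laboratory tests, ECGs, supine vital signs and eye assessments. SAP 3.2.2 repeats it: "Absolute values, changes from Baseline and incidence of potentially clinically significant changes in". Protocol 8.6 adds "Changes from baseline in laboratory parameters (including bone and calcium markers), vital signs, ECG and eye examinations data will be summarized by visit", although its sentence on the incidence of potentially clinically significant values names only laboratory and ECG values.

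SAP 6.7 converts acuity to LogMAR, derives changes at each visit in best corrected visual acuity (BCVA) and spherical equivalent, and states: "A change of 0.3 LogMAR (equivalent to 15 letters or 3-line change) is considered meaningful". For LOCS III it derives changes and, per subject, a worst change: "The largest increase from baseline (or smallest decrease if both eyes show a reduction from baseline) across the eyes".

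SAP 12.7 then summarizes "Observed and change from baseline values for the 4 cataract gradings in LOCS III", across both eyes and for the worst change. The remaining output is listings: "Eye examination data will be listed separately - refraction, BCVA, pinhole visual acuity, slit lamp examination, cataract grading, tonometry and irido-corneal drainage angle assessment". SAP section 14 declares no changes from the protocol's planned analyses.

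On when a grade exists, Protocol 7.1.6 says: "If the lens is clear, that should be recorded. If a cataract is identified, the cataract should be" classified and graded on LOCS III.

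**The concern.** There are two separate problems.

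1. **The incidence component of the endpoint has no table.** This does not depend on how lenses are coded. The SAP sets an acuity threshold and derives the variables it needs, but never counts subjects who cross it.

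2. **The change summaries cannot show new cataracts as the text stands.** Change is visit value minus baseline value (SAP 8.2). A lens recorded as clear has no stated grade, and Protocol 8.6 rules out imputation except for missing AE information. A cataract forming in a clear eye therefore gives no change value.

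Cataract in a rat toxicology study is the stated reason for the eye examinations (Protocol 1.4.2.2), and cataract is an adverse event of special interest (AESI). In a study whose primary objective is long-term safety, a reader will ask what proportion of subjects developed a new cataract on examination or lost a meaningful amount of acuity. No planned table answers either question.

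**Working it through.** **Step 1. Compare the four domains listed under the same endpoint.**

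| Domain | Count of subjects planned in the SAP |
|---|---|
| Laboratory | 12.2: criteria for CK, aldolase, troponin I and potential Hy's Law |
| ECG | 12.5: QTcF value and QTcF increase categories |
| Vital signs | 12.4: blood pressure change categories, number and percentage |
| Eye | 12.7: none |

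**Step 2. Reproduce the SAP's own eye arithmetic.** For 20/15-1, log10(15/20) + 0.02 = -0.105. For 20/15+1, log10(15/20) - 0.02 = -0.145. At 0.02 LogMAR per letter, 0.3/0.02 = 15 letters. All agree with SAP 6.7, so the acuity derivation and its threshold can be used as they stand.

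**Step 3. Apply the LOCS III rules to four invented eyes.** A dash means clear, hence no grade.

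| Eye | Baseline | Visit | Change |
|---|---|---|---|
| A | 2.0 | 2.0 | 0.0 |
| B | 1.5 | 1.5 | 0.0 |
| C | – | 2.5 | none |
| D | – | – | none |

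The change table has n = 2 and mean 0.0. The observed table has n = 3. The new cataract in eye C is missing from the change summary. If A and C belong to one subject, that subject's worst change is 0.0. A clear-to-graded count would report 1 of 2 clear eyes. If clear were scored 0, which neither document says, the mean change would be 2.5/4 = 0.625.

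**Step 4. Check the SAP 8.2 identity** that mean change equals mean observed minus mean baseline. Take g eyes stable at grade a, and m newly graded eyes at grade b. The mean change is 0. Observed mean minus baseline mean is (g·a + m·b)/(g + m) - a = m(b - a)/(g + m). With assumed g = 20 and a = 2.0:

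| m | b = 1.0 | b = 3.0 |
|---|---|---|
| 2 | -2/22 = -0.09 | +2/22 = +0.09 |
| 20 | -20/40 = -0.50 | +20/40 = +0.50 |

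The identity fails in every case, and new low-grade cataracts would pull the observed mean down.

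**Step 5. Scale.** The documents give no cataract rates, so these are assumptions. The planned number is about 150 mtDNA plus up to 50 nDNA subjects, 200 in all. If 1%, 3% or 5% develop a cataract in one previously clear eye, that is 200 × 0.01 = 2, 200 × 0.03 = 6 or 200 × 0.05 = 10 subjects. Those eyes contribute 0 LOCS III change values in each case.

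**Step 6. What an n/N row would show if no new cataract occurred.** The exact two-sided 95% upper limit for 0/n is 1 - 0.025^(1/n): 1.8% for n = 200, 2.4% for n = 150 and 7.1% for n = 50. This takes every subject to have at least one clear eye at baseline. Fewer eligible subjects would raise the limits.

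**The case against.** The strongest reply is that eye incidence is already counted through adverse events. SAP 6.7 makes any clinically significant eye abnormality an AE. Cataract formation or exacerbation after baseline is an AESI, reported in the same manner as an SAE, and SAP 12.1 tabulates subjects with AESIs overall, by term and by time period. Part of this stands: new cataracts would not be invisible, and they would also appear as added values in the observed LOCS III grades and in listings. But AEs and AESIs are primary endpoints, listed separately from this one. The AESI definition merges formation with exacerbation. Protocol 7.1.1.3 and 7.1.1.4 ask that worsening be worded as such, which separates the two only when listings are read. No AESI covers acuity loss, and since Protocol Version 3.0 a spherical-equivalent loss of at least 0.75 diopters is no longer routinely an AESI (SAP 6.1).

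A second reply is that Protocol 8.6 limits its incidence statement to laboratory and ECG values. That is true, so the mismatch begins inside the protocol. It does not remove eye assessments from section 3.2.2 of either document, and Protocol 8.6 still says that eye examination changes will be summarized by visit. The SAP does this for LOCS III only.

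A third reply is that the eCRF may give a clear lens a number. If so, the missing-change, worst-change and identity points all fall away. The first problem does not. The identity point is also a general SAP convention that any missing baseline would break; here the gap would be systematic, because it occurs whenever a cataract is new.

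Finally, the rates and grades in Steps 4 and 5 are assumed. They illustrate the mechanism and are not evidence of harm. An upper limit could also be computed from a zero AESI count, though its denominator would not be subjects with an examined clear eye.

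**Conclusion.** The concern holds. Followed exactly, the plan leaves the incidence part of a stated secondary safety endpoint without a table for eye assessments, leaves acuity and refraction changes unsummarized, and declares no change from the protocol. That conclusion needs no assumption about lens coding. The LOCS III point holds on the text of both documents and depends on the eCRF not assigning a grade to a clear lens. On that reading, every cataract that forms in a clear eye is absent from the change summary, and a stable fellow eye can make the subject's worst change read 0. The number affected cannot be estimated from the documents; 2 to 10 of 200 subjects corresponds to assumed rates of 1% to 5%. No hypothesis test is affected. This should be corrected before database lock.

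**What to change.** 1. In SAP 12.7 add, by group, by visit and at any time on treatment, an eye-level shift from baseline (clear or cataract), and n/N (%) of subjects with a new cataract in any eye clear at baseline. The denominator is subjects with at least one clear eye at baseline and a post-baseline examination of that eye.
2. Summarize BCVA and spherical-equivalent change by visit, and give n/N (%) of subjects whose BCVA worsens by at least 0.3 LogMAR in either eye, using the SAP's own threshold.
3. State in SAP 6.7 and 12.7 how a clear lens enters the LOCS III change, the worst change and the SAP 8.2 identity. If it has no grade, label the change summary as progression in eyes graded at baseline.
4. If these outputs will not be produced, record in SAP section 14 that the eye incidence endpoint and the by-visit acuity and refraction summaries are omitted, and why.

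The cost is SAP wording and one or two extra tables from data already collected, with no new visit or procedure. The drawbacks are small counts in the nDNA and Group 3 and 4 columns, and a shift table that depends on examiners recording clear and cataract consistently.
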